2.2.4 Treatment Group Assignments or Randomization

The study will be double-blind. The investigator, subjects, and sponsor personnel involved in the monitoring or conduct of the study will be blinded to the identity of the treatment from the time of randomization until the time of unblinding.

Subjects will be assigned to study treatment via appropriate randomization methods, in accordance with the randomization schedule generated by the allocation vendor (), prior to the start of the study, using validated internal software. Once a

CONFIDENTIAL Page 10 of 33

) will prepare the randomization schedule before the study. Enrolled, eligible subjects will receive a kit containing study gels according to an allocation table that randomly assigns subjects by order of enrollment to receive study gel for in 1 of 2 treatment arms (A or B). Separate allocation tables will be prepared for 120 male and 120 female subjects. Male or female enrollment may exceed the target sample size (n=120 each gender) by ±10%. If the target sample size is exceeded in one gender, the next available kit number in the other gender will be assigned.

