2.2.6 Interim Analysis for Futility Assessment

. The interim analysis will assess the futility of the trial (conditional power <0.05) based on efficacy of K-285 to menthol gel using the FAS. That is, if the conditional power is less than 0.05 (i.e., < 5%), the study would have met the stopping rule/decision criteria to stop for futility. The conditional power will be calculated under the assumption that the effect size estimate at the interim analysis is true. See Section 11 of SAP for more details.

An independent team of biostatisticians and statistical programmers will perform the interim analysis within a folder that has restricted access to only the independent team members to maintain the blinding of the study.

Interim analysis was conducted using 120 randomized subject data on Feb 26, 2021. The study has met the stopping rule to stop for futility because the conditional power is less than 0.05. As a result, 126 subjects randomized before the interim analysis will be included in final analysis, rather than the planned 240 subjects.

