8.3 Analysis Method for the Primary Efficacy Endpoint

The primary efficacy endpoint for this study is the sum of PID between () for the study leg after the first study gel application while standing using a 0-100 point eVAS. The primary analysis of the primary endpoint will be based on the FAS.

CONFIDENTIAL Page 17 of 33

The durations between nominal time points will be calculated using the actual times of the pain score measurement. If the actual time is missing the nominal planned time will be used.

The primary endpoint will be analyzed using an ANCOVA model, which will include treatment and gender as fixed effects and baseline eVAS score as a covariate. The least square (LS) mean, standard error (SE) and associated 95% confidence interval (CI) for each treatment group will be estimated. In addition, the LS mean difference between each treatment group, SE, p-value and the associated 95% CI will also be computed. Descriptive summaries (including mean, SD, median, minimum, and maximum) will also be presented. Missing data imputation methodology is described in Section 8.2 in this SAP.

Distributional assumptions underlying the model used for analysis will be examined by obtaining a normal probability plot of the residuals and a plot of the residuals versus the fitted values (i.e., checking the normality assumption and constant variance assumption of the model respectively) to gain confidence that the model assumptions are reasonable. A nonparametric test may be conducted if the normality assumption is violated. An ANCOVA with unequal variances may be conducted if the constant variance assumption is violated.

To explore the impact of collecting e-diary data from different vendors, a sensitivity analysis by including both baseline eVAS score and the e-diary vendor in the model will be performed. Since majority of the eVAS data are collected by the second vendor, an analysis based on the second vendor's data only will be performed also.

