8.4 Analysis Method for the Secondary Efficacy Endpoints

SPID Outcome	28
--------------	----

For non-study leg, after the first study gel application while standing using a 0-100 point eVAS, will be calculated, summarized, and analyzed similarly to primary endpoint.

The following secondary efficacy SPID outcomes are calculated and analyzed similarly to primary endpoint of sum of PID between for the study leg after the first study gel application while standing using a 0-100 point eVAS, adjusting for the respective time periods:

- SPID0-24 hours after the first study gel application at rest using a 0-100 point eVAS
- SPID between 0 (Baseline) to 12 hours (SPID0-12) after the first study gel application while standing using a 0-100 point eVAS
- SPID0-12 hours after the first study gel application at rest using a 0-100 point eVAS
- SPID between 0 (Baseline) to 48 hours (SPID0-48) after the first study gel application while standing using a 0-100 point eVAS
- SPID0-48 hours after the first study gel application at rest using a 0-100 point eVAS
- SPID between 0 (Baseline) to 72 hours (SPID0-72) after the first study gel application while standing using a 0-100 point eVAS
- SPID0-72 hours after the first study gel application at rest using a 0-100 point eVAS

CONFIDENTIAL Page 18 of 33

Change from Baseline in PID

The Mean change from Baseline in pain intensity difference (PID) while standing and rest at different time points, after the first study gel application using a 0-100 point eVAS, will be summarized descriptively.

Time-specific mean change from baseline in PID will be assessed using a mixed model repeated measures (MMRM) with PID as the dependent variable. Fixed effects of the model include treatment arm, time, the treatment arm by time interaction, baseline eVAS, and gender. Subject is a random effect. A completely general (unstructured) covariance matrix will be used. A first-order autoregressive covariance matrix will be used if the model with an unstructured covariance matrix does not converge. Pairwise comparisons at each time point will be determined from the MMRM, and model-based means (LS means) and standard errors will be plotted for visual comparison of the treatment group outcomes. Only scheduled measurements will be included in the MMRM.

Perceptible and Meaningful Pain Relief

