Pain assessments of time to first perceptible pain relief and time to meaningful pain relief for both legs at rest and while standing will be recorded by subjects using their e-diary. At the time of first perceptible pain relief and at the time of meaningful pain relief, subjects will use their e-diary to record the time the events are experienced. Since these assessments will be captured in the e-diary, the electronic database will be the direct point of data capture and will serve as source for this variable.

Both time to perceptible and meaningful pain relief will be analyzed using Kaplan-Meier curves with the log-rank test. Subjects will be censored at the time of safety visit on Day 8 or at the time of dropout. Estimated median time to perceptible/meaningful pain relief as well as their 95% confidence intervals will be tabulated by treatment group along with the number and percent of subjects censored.

Rescue Medication Usage

CONFIDENTIAL Page 19 of 33

The proportion of subjects receiving rescue medication will be summarized descriptively by treatment group, using counts and percentages, along with 95% confidence intervals and CMH chi-square or Fisher exact *p*-values.

Time to first administration of rescue medication is the date/time of the earliest rescue medication use minus the date/time of administration of study drug. If the subject receives no rescue medication, then the value will be censored at 168 hours or at dropout.

Time to rescue medication will be analyzed using Kaplan-Meier curves with the log-rank test. Estimated median time to first use of rescue as well as its 95% confidence interval will be tabulated by treatment group along with the number and percent of subjects censored.

Total (mg) rescue medication used will be summarized descriptively. For each summary period
, the mean number of rescue medication per day and the percentage of rescue-free days will be calculated. For each period and overall, cumulative rescue medication use will be displayed. Any data recorded after 168 hours, will not be included in any summaries.

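### The log-rank tests omit gender, the randomization stratum, and lose power if gender is prognostic; separately, the MMRM carries a redundant random subject effect and its only fallback, AR(1), forces equal variance at every time

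*SAP*

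**What the plan says.** Gender is the randomization stratum. SAP 2.2.4 (and Protocol 6.1) states: "Separate allocation tables will be prepared for 120 male and 120 female subjects". The primary ANCOVA in SAP 8.3 respects this with a model "which will include treatment and gender as fixed effects and baseline eVAS score as a covariate". The MMRM in SAP 8.4 and the leg-comparison model in SAP 8.5 also include gender.

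The time-to-event analyses in SAP 8.4 do not. For relief onset: "Both time to perceptible and meaningful pain relief will be analyzed using Kaplan-Meier curves with the log-rank test". For rescue: "Time to rescue medication will be analyzed using Kaplan-Meier curves with the log-rank test". Neither sentence names a stratum or covariate.

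For the MMRM of PID, SAP 8.4 says: "Subject is a random effect. A completely general (unstructured) covariance matrix will be used". One fallback follows: "A first-order autoregressive covariance matrix will be used if the model with an unstructured covariance matrix does not converge". The results used are per-time contrasts: "Pairwise comparisons at each time point will be determined from the MMRM".

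SAP 2.2.6 records that the trial met its futility rule, so that "126 subjects randomized before the interim analysis will be included in final analysis", against 240 planned.

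**The concern.** **Log-rank tests.** The trial balances the arms within gender, and the linear models use that balance. An unstratified log-rank test ignores it. If gender affects the time to relief or rescue, pooling men and women dilutes the treatment hazard ratio, while the test's variance takes no credit for the balance. The test then rejects too rarely under the null and loses power. With 126 subjects there is little power to spare.

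**MMRM.** Two points differ in weight.

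- A random subject effect adds one common variance to every element of the covariance matrix. An unstructured matrix already allows that, so one parameter cannot be identified. A converged fit is not biased. The redundancy may make non-convergence likelier, but how often was not estimated.
- Non-convergence triggers AR(1), which has a single variance for all times. If the spread of PID changes between 1 h and 168 h, the standard errors at single time points are too wide at some times and too narrow at others, and those contrasts are what the model is used for. Unequal visit spacing is not the issue here.

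**Working it through.** **1. Inputs from the documents.** Randomization 1:1 within gender; 126 subjects in the final analysis; two-sided 0.05 (SAP 8.2, stated for the primary analysis); relief times censored at the Day 8 visit or dropout, and rescue at 168 h or dropout (SAP 8.4). The only sizing figure is for the primary endpoint (Protocol synopsis): difference 11.07, SD 25.62, power 90%, 113 per group. It reproduces:

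n = 2 × (1.960 + 1.282)² × (25.62 / 11.07)² = 112.6, rounded up to 113.

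Nothing is sized for the log-rank or MMRM analyses.

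**2. Assumptions.** The documents give no hazard ratio for treatment or gender, no event rate, no split of the 126 by gender and no SD by time, and the assessment schedule is redacted. Assumed: treatment HR 1.6; median relief 24 to 48 h; exponential times; 62 men and 64 women; 5% random dropout; censoring at 168 h; gender HR 1 to 3.

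**3. Log-rank power.** Check with no gender effect: power = Φ(ln 1.6 × √(D/4) − 1.96). The simulations gave about 113 to 125 relief events. At the midpoint, D = 119: Φ(0.470 × 5.454 − 1.96) = Φ(0.60) = 73%. The simulation (40,000 trials per setting) gives 72–73%. Full results for relief:

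| Gender HR | Power, unstratified | Power, stratified | Null rejection, unstratified |
|---|---|---|---|
| 1 | 72–73% | 71–72% | – |
| 1.5 | 70% | 71–72% | – |
| 2 | 64–66% | 70–72% | 4.3% |
| 3 | 55–57% | 69–72% | 3.0% |

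Null rejection of the stratified test is 5.2–5.5%. For rescue at about 25% use (32 events, gender HR 2), power is 24.7% unstratified and 25.7% stratified.

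A second simulation used other assumptions: 15% censored in the control arm, and treatment HR set for about 80% power by HR = exp(2.80 / √(D/4)) with D = 0.85N. This gives HR 1.73 at N = 124 and 1.48 at N = 240.

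| Gender HR | N = 124, unstratified / stratified | N = 240, unstratified / stratified |
|---|---|---|
| 1.5 | 81% / 82% | 80% / 82% |
| 2 | 77% / 81% | 76% / 81% |
| 3 | 69% / 81% | 67% / 81% |
| 4 | 61% / 80% | 59% / 81% |

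The pattern is the same: little is lost up to HR 1.5, and the loss is material from about 2.

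**4. Redundancy of the random effect.** Write the total covariance as Σ = R + s·J, where R is unstructured, J is a matrix of ones and s is the subject variance. For any s that leaves Σ − s·J positive definite, R = Σ − s·J gives the same Σ. In a 4 × 4 example, s = 0, 20, 40 and 60 all reproduce it exactly. With 15 assumed times, unstructured has 15 × 16 / 2 = 120 parameters. The information matrix has rank 120 of 120 alone, and 120 of 121 once the subject effect is added.

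**5. AR(1) under unequal variance.** With one common SD used at every time, the per-time error is approximately 2 × [1 − Φ(1.96 × SD_model / SD_true)]. For a true SD rising from 15 to 25, the large-sample AR(1) fit has SD 20.75:

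- first time: 1.96 × 20.75 / 15 = 2.71, error 0.7%
- last time: 1.96 × 20.75 / 25 = 1.63, error 10.4%

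REML fits to 1,000 simulated null trials per SD path (126 subjects, 5% intermittent missing, 10% dropout; Monte Carlo error about 0.7 points at 5%) agree:

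| Assumed SD path | Type I error, 1 h | Type I error, 168 h |
|---|---|---|
| 15 to 25 | 0.9% | 10.5% |
| 20 to 25 | 2.8% | 8.3% |
| 25 to 15 | 11.0% | 0.7% |
| constant | 5.2% | 5.9% |

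With sandwich standard errors the same fits give 3.3% to 5.5% in all four cases.

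**6. Is a changing SD plausible?** The model adjusts for baseline. If raw pain has constant SD, the residual SD is proportional to √(1 − r²), where r is the correlation with baseline. If r falls from 0.9 to 0.69 (assumed), the ratio is √(1 − 0.476) / √(1 − 0.81) = 0.724 / 0.436 = 1.66, close to the 15-to-25 path. This shows plausibility only; the documents give no such correlations.

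**The case against.** **No error is shown, and the loss is hypothetical.** The unstratified test is valid, the documents do not say how prognostic gender is, and at HR 1.5 or below the gain is negligible. That stands. But the trade is uneven: stratifying costs about 1 point if gender is irrelevant, and regains about 6 points at gender HR 2 and about 14 at 3. For rescue the gain is about 1 point, and the case there rests on consistency.

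**The stratified test is slightly liberal, so the power gain is partly a size difference.** At 5.2–5.5% null rejection with Monte Carlo error √(0.05 × 0.95 / 40,000) = 0.11 points, a small excess is real. A separate simulation with 126 subjects and HR 1.6 gave stratified size of 5.2–5.3% and power of 65% against 72% at gender HR 2, and 57% against 71% at 3. The excess explains little of the gain.

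**The written fallback is AR(1) plus a random subject effect, which is identifiable there.** True, but a random intercept adds the same constant at every time, so the variance stays constant. The per-time error is distorted in the same way with or without it (0.8% and 11% for SD 15 to 25).

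**The harm needs both non-convergence and drifting variance, and neither probability is known.** This stands as a limit on size. Against it, an unstructured fit with 120 covariance parameters (at 15 assumed times) and 126 subjects is not certain to converge, so the fallback should be sound.

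**The remedy goes beyond the evidence.** In part this stands: the 3.3–5.5% result comes from AR(1) fits with sandwich errors. The heterogeneous structures were not simulated; they are standard choices.

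**The trial has already met its futility rule.** Also fair: only secondary results are at stake, and a change made now should be dated as following the interim result.

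**Conclusion.** The point holds, as a should-fix matter for secondary analyses. The primary ANCOVA and the SPID analyses are untouched.

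- **Log-rank:** valid but conservative if gender is prognostic. The power loss for relief is at most 2 points at gender HR 1.5, about 6 at 2 and about 14 at 3, given 126 subjects and treatment HR 1.6. For rescue it is about 1 point at gender HR 2.
- **Random subject effect:** redundant under the unstructured matrix and harmless once the model converges. Its effect on convergence is unknown.
- **AR(1) fallback:** if it is used and the SD changes by the assumed amounts, per-time type I error at the two ends runs from about 1% to about 11% instead of 5%. Which end is inflated depends on whether the spread grows or shrinks. With constant SD there is no material problem.

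The hazard ratios, event rates, gender split, time points and SD paths are assumptions. Confidence in the sizes is therefore moderate. The structural statements need none of these assumptions.

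**What to change.** In SAP 8.4:

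1. Stratify the log-rank tests for perceptible relief, meaningful relief and rescue by gender.
2. Delete the sentence that makes subject a random effect. Use subject only as the clustering unit of the unstructured residual covariance.
3. Replace the AR(1) fallback with a prespecified order of structures that let variance differ by time: heterogeneous Toeplitz, then heterogeneous compound symmetry, each with sandwich standard errors.
4. Record that these changes were made after the interim result.

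The cost is SAP wording and SAS options, with no new data. The downsides are about 1 point of power in the relief tests if gender is not prognostic, almost no gain for rescue if few subjects use it, stratified null rejection marginally above 5% in simulation, and some small-sample noise in the sandwich errors (3.3% to 5.5% in the AR(1) fits).

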4.3.1 Discontinuation due to an Application Site Reaction

1. During a clinical site visit, the application site reaction will be assessed by study staff. If there are any significant findings, they will be noted in each subject's source documents.
 - If the application site reaction is judged to meet the discontinuation criteria ([Section 4.3](#)), the subject will be discontinued from the study.
2. During the out-patient period at home, application site reactions will be assessed by the subject. If any application site reaction is noticed, the subject will contact the site before dosing.
 - The subject will not apply study gel until receiving confirmation from the site to proceed.
 - If the subject contacts the site and then the application site reaction is judged to meet the discontinuation criteria ([Section 4.3](#)), the subject will be discontinued from the study. At that time, the subject will be asked to gather safety reference information as follows:
 - Record the score of dermal response ([Section 5.2.6](#)) in the e-diary. Reference images of application site reactions are shown in [Appendix 15.4](#).

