5.1.3 Time to Onset of First Perceptible and Meaningful Pain Relief

Pain assessments of time to first perceptible pain relief and time to meaningful pain relief for both legs at rest and while standing will be recorded by subjects using their e-diary until achieved in Period 1. At the time of first perceptible pain relief and at the time of meaningful pain relief, subjects will use their e-diary to record the time the events are experienced. Since these assessments will be captured in the e-diary, the electronic database will be the direct point of data capture and will serve as source for this variable.

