10.5 SUBJECT DISCONTINUATION AND WITHDRAWAL

If a subject experiences an AE that leads to discontinuation of study gel treatment and withdrawal from the study, the CRF/eCRF will identify the AE as the reason for withdrawal. Subjects that discontinue study gel treatment will be asked to continue scheduled study visits through the Follow-up phone call.

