8.2 Handling of Dropouts or Missing data

CONFIDENTIAL Page 16 of 33

Missing VAS values up to 168 hours caused by early withdrawal from the study due to events which are not preferable to subjects such as an adverse event (AE) and/or lack of efficacy (LOE) will be imputed by last observation carried forward (LOCF).

If missing VAS values caused by withdrawal other than AE and/or LOE will be imputed for each treatment group separately under the missing at random (MAR) assumption with the multiple imputation (MI) technique. The imputation will be carried out in SAS version 9.4 or later, using the full conditional specification method (FCS) with a regression model approach (Carpenter and Kenward, 2013). By using the MI technique, 100 datasets will be generated. After calculating the SPID, an analysis of covariance (ANCOVA) model will be applied for the primary endpoint with gender and treatment as fixed effects and baseline pain as a covariate in each dataset. Multiple results will be combined using Rubin's rule (Little and Rubin, 1987), and will be done in SAS using PROC MIANALYZE. A significance test of the treatment difference at the two-sided 0.05 level and corresponding 95% confidence intervals will be calculated. However, the multiple imputation is used only for subjects that have a baseline.

If there exist missing VAS values to be imputed, any such values will be imputed before calculating the SPID. Intermediate missing VAS values due to an omission of recording pain intensity or subject's sleep will not be imputed, therefore, the observed values before and after the missing measurement will be directly connected in order to calculate the SPID. If subjects need to take the rescue medication, they will record their pain intensity in the eDiary before taking the rescue medication. If the rescue medication is taken within 6 hours of a nominal pain intensity assessment time point, the pain intensity score that was recorded before taking the rescue medication will be carried forward to the next pain intensity assessment time point.

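### Time to pain relief: censoring lack-of-efficacy withdrawals at dropout overstates the Kaplan-Meier relief curves, and biases the log-rank comparison if such withdrawals differ between arms

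*SAP*

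**What the plan says.** SAP section 8.4 (Perceptible and Meaningful Pain Relief) names the method: "Both time to perceptible and meaningful pain relief will be analyzed using Kaplan-Meier curves with the log-rank test". The censoring rule follows: "Subjects will be censored at the time of safety visit on Day 8 or at the time of dropout". Medians with confidence intervals and the number and percentage censored are tabulated by arm. The section does not split censoring by reason and describes no sensitivity analysis of the rule.

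Protocol section 5.1.3 says that relief times "will be recorded by subjects using their e-diary until achieved in Period 1", so a subject without an entry at exit has reported no relief.

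SAP section 8.2 does separate withdrawals by reason, but only for eVAS values. It describes one class as "Missing VAS values up to 168 hours caused by early withdrawal from the study due to events which are not preferable to subjects", names adverse event (AE) and lack of efficacy (LOE) as examples, and says that these values "will be imputed by last observation carried forward (LOCF". Values missing through other withdrawals are multiply imputed under missing at random.

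Two protocol passages bear on who counts as a dropout. Section 10.5 states: "Subjects that discontinue study gel treatment will be asked to continue scheduled study visits through the Follow-up phone call". Section 4.3.1 says of an application-site reaction that meets the criteria: "the subject will be discontinued from the study".

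**The concern.** Kaplan-Meier and log-rank methods assume that, within an arm, a censored subject has the same future chance of the event as those still at risk. A subject who withdraws for LOE without having reported relief breaks that assumption by definition: the exit happens because the event has not. Each such censoring removes a non-responder from the denominator, and the later steps of the relief curve become too large.

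The relief curves and their medians are at stake and, if one arm loses more subjects this way, so is the log-rank result. Relative to an analysis that counts these subjects as unrelieved, the rule favours the arm with more LOE withdrawals. A time-to-relief result could then differ from the SPID result because of the censoring rule alone.

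**Working it through.** **The plan's own figure.** The documents give no number for the time-to-relief analyses. The primary sample size reproduces with two-sided alpha 0.05 and 90% power: n = 2 × (1.960 + 1.282)² × 25.62² / 11.07² = 112.6, so 113 per group. The step from 113 to 120 allows (120 − 113)/120 = 5.8% for missing data of every kind, not split by reason or arm. SAP section 2.2.6 puts 126 subjects in the final analysis, about 63 per arm if evenly split.

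**Assumed inputs.** A share w withdraws for LOE before any relief, at times uniform on a stated interval. G(t) is the proportion of these still present at t. Relief in the others is exponential with a 24-hour median, S(t) = 2^(−t/24).

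**Formulas.**
- As written: hazard in the risk set h(t) = λ(1−w)S(t) / [(1−w)S(t) + wG(t)], with λ = ln 2/24. Expected Kaplan-Meier relief = 1 − exp(−∫h).
- LOE withdrawals kept unrelieved to 168 h: relief = (1−w)(1−S(t)).

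Worked case, w = 10%, exits at 12–24 h. Retained: 0.9 × 0.5 = 0.450 at 24 h; 0.9 × 0.875 = 0.788 at 72 h. As written: numerical integration gives 0.465 at 24 h. All withdrawers have then gone, so the unrelieved proportion at 72 h is 0.535 × 0.25 = 0.134, and relief is 0.866.

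Cumulative relief, as written / retained:

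| LOE exits | 6 h | 24 h | 72 h | 168 h | Median (h) |
|---|---|---|---|---|---|
| 3%, at 12–24 h | 0.154 / 0.154 | 0.490 / 0.485 | 0.872 / 0.849 | 0.992 / 0.962 | 24.7 / 25.1 |
| 5.8%, at 12–24 h | 0.150 / 0.150 | 0.480 / 0.471 | 0.870 / 0.824 | 0.992 / 0.935 | 25.4 / 26.2 |
| 10%, at 12–24 h | 0.143 / 0.143 | 0.465 / 0.450 | 0.866 / 0.788 | 0.992 / 0.893 | 26.4 / 28.1 |
| 10%, at 24–168 h | 0.143 / 0.143 | 0.450 / 0.450 | 0.799 / 0.788 | 0.954 / 0.893 | 28.1 / 28.1 |

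With slower relief (80% of the others by Day 8) and 5.8% exits, Day 8 relief is 75.4% retained. As written it is 77.9% with exits over 24–168 h and 79.9% with exits in the first 24 h.

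**Log-rank test, simulated, 63 per arm.**
- Equal LOE withdrawal, 5.8% in each arm: one-sided rejection is 2.6–2.9% against a nominal 2.5%, so there is no material distortion.
- LOE withdrawal 2% on K-285 and 10% on menthol, exits at 12–24 h, same 24 h median in the others: mean Z in favour of K-285 is about 0.25 as written and 1.3 retained. If the K-285 median is also set to 18 h, power is 43% against about 70%.
- Withdrawal 10% against 2% with true Day 8 relief set to 75% in both arms (withdrawers counted as unrelieved): the test favours the arm with more withdrawals in 8.1–16.0% of runs as written, against 3.8–4.3% retained.

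**AE withdrawals.** Suppose instead that exits are for AEs unrelated to soreness, 10% on K-285 and 2% on menthol at 12–24 h, with no treatment difference. Two-sided rejection is about 5% as written. Keeping those subjects unrelieved to 168 h raises it to about 11%, with mean Z of −0.73 against K-285.

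**The case against.** **AE exits differ from LOE exits.** A reader might infer from section 8.2, which groups the two, that censoring AE withdrawals also overstates relief. The documents do not support that. The specific AE stopping criteria in Protocol sections 4.3 and 4.3.1 are largely skin findings, which need not relate to soreness. For such exits the current rule can be the unbiased one, and retention creates the bias shown above. This objection stands.

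**Sections 8.2 and 8.4 are not in strict contradiction.** One might say that the SAP makes opposite assumptions about the same subject. But LOCF carries a last score that may already be below baseline, and it is confined to eVAS values. Different endpoints may rest on different missing-data assumptions; the MMRM already uses scheduled measurements only. What remains is that 8.4 gives no reason for treating LOE exits as uninformative.

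**Size and visible outputs.** The titles of Tables 14.2.9.1 and 14.2.9.2 cover relief by 6 and 24 hours, where the shift is nil or small. Access to rescue for severe pain and continued visits after stopping gel may keep LOE dropouts few, and 10% in one arm exceeds the whole 5.8% allowance. Exits spread over 24–168 hours leave the median unmoved and shift the 72-hour value by about 1 point, although the Day 8 end of the curve still moves by 6 points in the 10% case. Some table titles are redacted, so a supportive analysis cannot be wholly excluded.

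**Rescue endpoint and Day 8 wording.** Time to rescue might look like a better model because it names 168 hours, but it is also censored at dropout; only its administrative limit is fixed. The reference to a Day 8 safety visit is loose rather than wrong: 1-week subjects also attend on Day 8, at a visit called end of study with a different window.

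**Conclusion.** The point holds for LOE withdrawals before relief. Censoring them at dropout overstates the relief curves, and it biases the log-rank contrast when such withdrawals differ between arms. It does not hold as a general statement about AE withdrawals.

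The size cannot be known from the documents. Under the assumptions above, the 72-hour overstatement runs from about 1 to 8 points, with the upper end needing 10% LOE exits, all within 12–24 hours. A reader might infer a known bias for or against K-285; nothing in the documents says which arm would lose more subjects, and with equal loss the contrast is essentially undistorted. The 43% against 70% power contrast rests wholly on assumed rates and medians.

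The analyses affected are secondary, and SPID0-24 is untouched. The change is still worth making because it is cheap and removes a censoring assumption that is implausible for LOE exits.

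**What to change.** Replace the censoring sentence in SAP section 8.4 with:

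> A subject who withdraws for lack of efficacy before reporting relief remains in the risk set without an event and is censored at 168 hours; all other subjects without relief, including AE withdrawals, are censored at last e-diary contact or 168 hours, whichever is earlier.

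Apply it separately to perceptible and meaningful relief, and state in advance which rule covers a withdrawal recorded as both AE and LOE. Report two sensitivity analyses: (a) the current rule, with all dropouts censored at dropout; (b) AE withdrawals also retained to 168 hours. Tabulate censoring by reason and arm. Say how dropouts count in Tables 14.2.9.1 and 14.2.9.2. Protocol sections 4.3.1 and 10.5 should be reconciled on whether a subject who stops gel leaves the study, because that decides who is a dropout.

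The cost is one SAP sentence, one change in the time-to-event dataset and a few table rows. Section 8.2 already needs the withdrawal reason. The downside is the assumption that LOE withdrawals get no relief to 168 hours, which is in line with their separate LOCF handling in 8.2. If the SAP can no longer be changed, section 1 lets the analysis be added and labelled post hoc.
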